### **2.6.4. Adverse Events**

A treatment-emergent adverse event (TEAE) is defined as an AE onset on or after the start of open-label treatment period through 7 days after study drug discontinuation (14 days for serious adverse events and deaths). For sake of simplicity, hereafter TEAE is referred as AE in the section.

The overall incidence (ie, number and percent of subjects with one or more AE in each category) of AEs, serious AEs, deaths, AEs leading to discontinuation, drug-related AEs, serious drug-related AEs, drug-related AEs leading to discontinuation, serious AEs leading to discontinuation, and serious drug-related AEs will be summarized by analysis group and by analysis subgroup, separately.

AEs by system organ class (SOC) (number and proportion of subjects with one or more AEs within a system organ class) will be summarized by analysis group. For each AE, the percentage of subjects who experienced at least one occurrence of the given event will be provided by preferred term, grouped by system organ class, and presented by analysis group and by analysis subgroup. AEs for age subgroup summary will be also presented by SOC and preferred term and by analysis group and analysis subgroup.

Furthermore, additional summaries will be created based on the following combined preferred terms:

- Dystonia - preferred terms: dystonia, trismus, oculogyric crisis, oromandibular dystonia, tongue spasm, torticollis
- Parkinsonism - preferred terms: bradykinesia, drooling, extrapyramidal disorder, glabellar reflex abnormal, hypokinesia, parkinsonism, psychomotor retardation
- Somnolence - preferred terms: hypersomnia, sedation, somnolence, hypersomnolence

According to MedDRA coding guidelines for Lurasidone pediatric program,

- EPS-related reported terms for Tremor, Rigidity or Muscle Rigidity will be queried for further specificity. Sites will qualify if the reported term is Parkinsonian or non-Parkinsonian in nature; if confirmed, the reported term will be coded to lowest level terms of Parkinsonism; if not, the term will be coded to specific symptom.
- For reported term Restlessness, sites will qualify if the reported term is Akathisia or non-Akathisia in nature; if confirmed, the reported term will be coded to lowest level terms of Akathisia; if not, the term will be coded to specific symptom.

In clinical database of this study, AEs with preferred term of Tremor, Muscle Rigidity, and Cogwheel Rigidity should be read as non-Parkinsonian; AEs with preferred term of Restlessness should be read as non-Akathisia. Due to above reasons, preferred terms Tremor, Muscle Rigidity, and Cogwheel Rigidity are not included in the list for combined preferred terms of 'Parkinsonism'. In addition, these three preferred terms plus term Restlessness are not included in the list for extra-pyramidal symptoms (EPS)-related AEs in [Attachment 4.5.1](#).

Summaries of AEs by preferred term only by analysis group for both combined and uncombined terms will be generated as well, respectively.

In addition, the incidence of AEs (by preferred term, grouped by SOC, and presented by analysis group and by analysis subgroup) will also be summarized by severity, by the relationship to study medication, by the action taken regarding the study medication, as well as by the outcome. The relationship to study medication will be presented by 2 categories: related (which includes possibly related, probably related, and related, as determined by investigators), and not related (which includes unrelated and unlikely to be related, as determined by investigators). Listings will also be generated for deaths, SAEs, and discontinuations due to AEs. All adverse events regardless of treatment emergent status will be provided in the AE data listing.

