11.4. Study Visits and Assessments

11.4.1. Visit 1E (Day 1)

Visit 1E (Day 1) – this visit will occur on the same day as Study Visit Number 9 in Study D1050301 and Study D1050325 and Study Visit Number 8 in Study D1050326.

Note: Assessments specific to this study are listed below; all other assessments will be carried over from Study Visit Number 9 in Study D1050301 and Study D1050325 and Study Visit Number 8 in Study D1050326.

- Obtain informed consent/assent
- Inclusion/exclusion criteria

- Interactive Voice/Web Response System (IXRS) subject registry/visit
- Dispense study medication

Clinical and Laboratory Evaluations: ALL SUBJECTS

- Prior/concomitant medication review
- Adverse event (AE) monitoring

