13. ADVERSE EXPERIENCE REPORTING

13.1. Adverse Events

An adverse event (AE) is any new, untoward medical occurrence or worsening of a pre-existing medical condition that occurs during study participation, whether or not the event is considered drug related.

AEs will be collected from the time the informed consent is signed to the end of the study. Serious adverse events (SAEs) will be collected and reported on the SAE form, from the time of informed consent to 14 days post last dose and will be followed until resolution or lost to follow up. SAEs occurring from the time of informed consent to the end of study must be recorded on the CRF and the data recorded should match that on the SAE form.

Non-leading questions will be used to ask subjects about the possible occurrence of AEs. The investigator should attempt to establish a diagnosis of the event based on signs, symptoms, and/or other clinical information. In such cases, the diagnosis should be documented as the AE and not the individual signs/symptoms.

Following questioning and evaluation, all AEs, whether believed by the investigator to be related or unrelated to the study medication, must be documented in the subject's study records/source documents, in accordance with the investigator's normal clinical practice, and on the AE page of the CRF. Each AE is to be evaluated for duration, intensity, seriousness, and causal relationship to the study medication. [Appendix C](#) (Definitions for Reporting Adverse Events) provides definitions for severity of an adverse event, relationship to study medication, frequency, and action taken. An AE is deemed associated with the use of the study drug "if there is a reasonable possibility that the experience may have been caused by the drug" (21 CFR 312.32 [a]).

The Medical Monitor is the initial contact person for protocol related questions or discussion of AEs. The contact information for the Medical Monitor as well as other emergency contact information can be found in [Table 1](#) of this protocol.

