14.4. Variables and Timepoints

14.4.1. Primary Safety Variables

The primary safety variables include treatment-emergent AEs and SAEs, and discontinuations due to AEs.

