14.7.4.2. Safety Evaluation

All safety evaluations will be summarized for all subjects by analysis group for the safety population.

Safety evaluations include:

- AEs, SAEs, Discontinuation due to AEs and SAEs;
- Laboratory safety tests (chemistry, including liver function tests and bilirubin; hematology including HbA_{1c}; serum lipids; glucose; hormonal parameters; and urinalysis);
- Body weight, height, BMI, waist circumference, vital signs, physical examinations, and ECG parameters;
- Simpson-Angus Scale (SAS);
- Barnes Akathisia Rating Scale (BARS);
- Abnormal Involuntary Movement Scale (AIMS);
- Tanner staging, and menstrual cyclicity (female subjects).

For subjects continued from Study D1050301 and D1050326:

- Columbia Suicide Severity Rating Scale (C-SSRS);
- CogState Cognitive Test Battery;
- Udvalg for Kliniske Undersøgelser Side Effect Rating Scale (UKU).

For subjects continued from Study D1050326:

- Young Mania Rating Scale (YMRS) score.

The primary analysis for the study is to assess the incidence of AEs, SAEs, and discontinuations due to AEs. The terms used in the eCRFs by investigators to identify adverse events will be coded using the Medical Dictionary for Regulatory Activities (MedDRA). All reported adverse events with onset on or after the first dose of study drug during the treatment phase (ie, treatment-emergent adverse events) will be included in the analysis.

AEs will be summarized by presenting the number and percentage of subjects having any AE, having an AE by body system, and having each individual AE. The incidence of an AE is determined by occurrence of at least one AE regardless of the frequency, severity and/or relationship to study medications. AEs will also be summarized by maximum severity and relationship to study medication (as assessed by the investigator), and action taken.

Special attention will be given to those subjects who discontinue treatment due to an adverse event, or who experienced a severe or a serious adverse event (eg, summaries, listings, and narrative preparation may be provided, as appropriate).

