#### **2.1.2. Definition of Open-Label Treatment Phase in Extension Study**

The day of the 1st dose date in the extension study will be denoted as study Day 1. All measurements at each visit will be assigned a study day relative to this date. All data collected on/after Day 1 for subjects previously randomized to placebo group in core study or on/after the extension baseline visit for subjects previously randomized to lurasidone groups up to Week 104, including the End-of-treatment/Early Withdrawal visit, will be considered within the open-label treatment phase. That is to say, the start of the open-label treatment period is defined as Day 1 for subjects previously randomized to placebo group and the OL Baseline visit date for subjects previously randomized to lurasidone groups; the end of the open-label treatment phase is defined as the maximum of the last date of administration of study medication and the withdrawal/completion date for subjects who have completed the study.

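### SAP 2.6.4 counts AE discontinuations only for events with open-label onset, so a core-study AE that persists unchanged and ends extension treatment is missing from that table and the count can disagree with disposition

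*SAP*

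**What the plan says.** SAP 2.6.4 defines the event by its start date: "A treatment-emergent adverse event (TEAE) is defined as an AE onset on or after the start of open-label treatment period". The window closes 7 days after study drug stops, or 14 days for serious events and deaths. The next sentence extends the rule to everything that follows: "For sake of simplicity, hereafter TEAE is referred as AE in the section". The overall incidence table in that section includes a line for AEs leading to discontinuation.

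SAP 2.1.2 fixes the start of the period. It is Day 1 for subjects who had placebo in the core study, and "the OL Baseline visit date for subjects previously randomized to lurasidone groups". Protocol 11.4.1 says of Visit 1E that "this visit will occur on the same day as Study Visit Number 9 in Study D1050301 and Study D1050325", and gives the matching rule for Visit 8 of D1050326.

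Protocol 14.7.4.2 is also onset-based: "All reported adverse events with onset on or after the first dose of study drug during the treatment phase" enter the analysis. The same section says "The primary analysis for the study is to assess the incidence of AEs, SAEs, and discontinuations due to AEs", and Protocol 14.4.1 says "The primary safety variables include treatment-emergent AEs and SAEs, and discontinuations due to AEs".

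Neither document has a rule for a core-study AE that is still present at open-label entry, or for one that later ends treatment.

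**The concern.** For subjects who had lurasidone in the core study, the extension continues treatment. An onset rule that restarts at roll-over fits a count of new events. It fits a count of treatment stops less well, because the stop happens in the extension whenever the event began.

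The primary objective is long-term safety and tolerability. An effect that begins early on drug, does not resolve and eventually makes the subject stop is part of that question. Under SAP 2.6.4 such a stop is not counted as an AE discontinuation. It is not a core-study discontinuation either, because Protocol 8.1 requires completion of the core study. The report could then carry two different numbers for one primary variable, one in the AE section and one in disposition, without explanation.

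**Working it through.** **Tracing one subject through the definitions.** Take an AE with onset during core-study lurasidone, unchanged at entry, with study drug withdrawn for it in the extension.

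1. *Start of window* (SAP 2.1.2, Protocol 11.4.1): the open-label baseline visit, on the day of the last core visit. The onset is earlier.
2. *TEAE status* (SAP 2.6.4): onset precedes the window, so it is not a TEAE. SAP 2.1.14.2.1 treats an event as treatment-emergent only when an incomplete date leaves its status undetermined, which is not the case here.
3. *AEs-leading-to-discontinuation line* (SAP 2.6.4): AE means TEAE, so it is not counted. Columns by prior treatment do not help, because the event is absent from the prior-lurasidone columns too.
4. *Disposition* (SAP 2.2.2.2, Protocol 12.1): reasons are summarised with no onset limit and adverse event is a coded reason. The subject is counted if that reason is recorded.
5. *Listings* (SAP 2.6.4): the full AE listing ignores treatment-emergent status. Protocol 13.1 collects AEs from extension consent, and the documents do not say whether ongoing core AEs are carried into the extension AE data, so the listing may be incomplete.

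If the event worsens after entry the result changes. Protocol 13.1 defines an AE as "any new, untoward medical occurrence or worsening of a pre-existing medical condition that occurs during study participation", so the worsening can have its own open-label onset and be counted. The gap is limited to events that persist unchanged.

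**Other safety outputs.** SAP 2.6.3 classes abnormal laboratory, vital-sign and ECG values by whether they meet the criteria within the open-label phase, with no new-onset condition. SAP 2.6.12 tabulates UKU side effects in the extension and compares them with the double-blind baseline. UKU covers D1050301 and D1050326 only: 271 + 306 = 577 of 702 subjects (82%), leaving out the 125 from D1050325. SAP 2.6.9 gives change from double-blind baseline for BARS, AIMS and SAS. None of these outputs counts treatment stops.

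**Size.** The plan gives no figure for this. Its enrolment total reproduces: 271 + 125 + 306 = 702 (Protocol 14.5). The rest is illustration, because the documents give no core allocation ratio, carry-over rate or stop rate.

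- Assume equal allocation and equal roll-over, with two of three arms on lurasidone in D1050301 and D1050325 and one of two in D1050326: 271 × 2/3 + 125 × 2/3 + 306 × 1/2 = 180.7 + 83.3 + 153 = 417, and 417/702 = 59%.
- Assume 5% to 20% of these have a lurasidone-onset AE ongoing at entry: 417 × 0.05 = 21 to 417 × 0.20 = 83 subjects.
- Assume 10% of those stop for it: about 2 to 8 subjects, or 0.3% to 1.2% of 702.

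**The case against.** The strongest reply is that a phase-specific onset rule is what the protocol prescribes. Protocol 14.7.4.2 uses it, and Protocol 6.1 speaks of TEAEs leading to discontinuation. That stands as a defence of the TEAE incidence tables, which should stay. It is weaker for the discontinuation count: Protocol 14.4.1 lists discontinuations due to AEs separately from treatment-emergent events, and the synopsis counts subjects terminated for AEs with no onset limit in that sentence. The protocol supports either reading, and the SAP takes the narrower one without saying so.

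A reader might infer that such events vanish from the extension's results. The documents do not support that. Disposition counts the stop if adverse event is the recorded reason, the full AE listing is not restricted by onset, a worsening counts as a new AE, and UKU picks up carried-over side effects in 301 and 326 subjects. What remains is that disposition gives a reason category without preferred term, severity or relationship.

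A reader might also take akathisia as the natural example. Protocol 8.2 excludes moderate or severe movement disorders at entry, so the akathisia would have to be no more than mild, not worsen and still end treatment. The investigator must also judge the subject suitable for a 104-week trial (Protocol 8.1). Both conditions reduce carry-over.

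Finally, it is tempting to say that prior-lurasidone subjects will look better tolerated than prior-placebo subjects. The plan makes no statistical comparison between treatment groups and shows overall AE incidence by prior treatment, so readers can see who had earlier exposure. That is not a reason to change the plan.

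**Conclusion.** The concern holds in a limited form. As written, the AEs-leading-to-discontinuation line in SAP 2.6.4 omits any stop caused by a core-study AE that persisted unchanged, and it can disagree with the disposition table on a primary safety variable. This follows from the definitions and needs no assumption.

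The size does not follow from the documents. The 417 entering on lurasidone depends on assumed equal allocation and roll-over, and the 2 to 8 missing stops depend on two further assumed rates. These show that the effect is probably small in absolute terms; they are not estimates. They should not be read as showing that most of the cohort is affected, or that carried-over tolerability problems go unrecorded.

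**What to change.** In SAP 2.6.4, count as an AE leading to discontinuation any AE recorded as leading to withdrawal of extension study drug, regardless of onset date. Protocol Appendix C already has drug withdrawn as an action-taken category. Split the count by onset: open-label, core study on lurasidone, core study on placebo. The placebo row is needed because a rule starting at first lurasidone dose would still leave the count out of step with disposition. State that the total will be checked against the disposition table and any difference explained. Keep the current TEAE tables as they are.

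As a supplement, tabulate by preferred term and prior treatment the AEs ongoing at open-label baseline, taken from the core datasets on which SAP 2.1.5 already draws. Report later status only where the extension AE data record it, because locked core records cannot show whether an event was still present at Week 52 or Endpoint.

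The cost is one extra table, a merge with core AE data and possibly a slightly higher AE-discontinuation count. SAP section 1 says the schizophrenia report is already complete, so for those subjects the change would appear in the full final report.

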### **AEs with Special Interest**

A list of preferred terms that are to be combined for the assessment of each of the pre-specified adverse events (including Extrapyramidal Symptoms (EPS)-related AEs, metabolic-related AEs, hypersensitivity-related AEs, and suicidality and self-injury related AEs) is provided in [Attachments 4.5.1 - 4.5.4](#). These AE preferred terms are determined and verified by medical review of coded AE terms during data review meeting and finalized prior to database lock. The incidence and exposure adjusted incidence rates of EPS-related AEs, metabolic-related AEs,

hypersensitivity-related AEs, and suicidality and self-injury related AEs will be summarized by analysis group and by analysis subgroup, respectively. In addition, EPS-related AEs will be summarized for akathisia and non-akathisia event as well.

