### **AEs by Exposure**

The TEAEs will be summarized by exposure to study drug using time intervals beginning with the earliest concurrent exposure to study drug for following AE summary as needed.

Denominators for exposure intervals will be based on the number of subjects who were exposed as of the first day of the interval; for cases where events meet the treatment-emergent definition but start after the last dose, the exposure interval for the event will be considered the interval of the last day of exposure to study medication.

- AEs by system organ class (SOC) and preferred term, Serious AEs by SOC and preferred term, and AEs leading to discontinuation by SOC and preferred term (sorted alphabetically by SOC and preferred term within SOC).
- AEs by preferred term, AEs with special interest by preferred term (sorted by descending order per frequency count)

Exposure category to be assessed is given below:

- Exposure categories : 1-13 days, 14-27 days, 28-55 days, 56-83 days, 84-167 days, 168-363, and  $\geq 364$  days.

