## 4.5. Selected Adverse Events with Special Interest

### 4.5.1. Extrapyramidal Symptoms (EPS)-Related AEs

BRADYKINESIA	PARKINSONISM
DROOLING	PSYCHOMOTOR RETARDATION
DYSTONIA	TORTICOLLIS
GLABELLAR REFLEX ABNORMAL	TRISMUS
HYPOKINESIA	PSYCHOMOTOR HYPERACTIVITY
OCULOGLYRIC CRISIS	AKATHISIA
OROMANDIBULAR DYSTONIA	DYSKINESIA
EXTRAPYRAMIDAL DISORDER	TARDIVE DYSKINESIA
SALIVARY HYPERSECRETION	

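### The EPS-related AE list (SAP Attachment 4.5.1) omits tongue spasm, which SAP 2.6.4 counts as dystonia, so a subject with only that event is missed from the EPS counts; the effect is small and possibly zero.

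*SAP*

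**What the plan says.** SAP 2.6.4 (Adverse Events) groups selected preferred terms for additional summaries. One group is "Dystonia - preferred terms: dystonia, trismus, oculogyric crisis, oromandibular dystonia, tongue spasm, torticollis"; another, Parkinsonism, has seven preferred terms.

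Attachment 4.5.1 separately lists 17 preferred terms that make up EPS-related AEs. It covers specific dystonic terms such as "OROMANDIBULAR DYSTONIA", but tongue spasm is not among the 17.

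SAP 2.6.4 explains certain absences from the EPS list. Tremor, muscle rigidity and cogwheel rigidity, where they remain as coded terms, are to be read as non-parkinsonian, and restlessness as non-akathisia. For that reason "these three preferred terms plus term Restlessness are not included in the list for extra-pyramidal symptoms (EPS)-related AEs". No other exclusion is explained.

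The EPS list then drives several outputs:

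- Under AEs with Special Interest: "The incidence and exposure adjusted incidence rates of EPS-related AEs, metabolic-related AEs" and the other special-interest groups are summarized by analysis group and subgroup.
- In the same place: "EPS-related AEs will be summarized for akathisia and non-akathisia event as well".
- Under AEs by Exposure, as needed: "AEs by preferred term, AEs with special interest by preferred term".

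The SAP also says that the special-interest terms are "determined and verified by medical review of coded AE terms during data review meeting and finalized prior to database lock".

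**The concern.** Two definitions in one plan disagree on whether tongue spasm is an extrapyramidal event. Section 2.6.4 treats it as dystonia. The attachment, which otherwise takes in every dystonia and parkinsonism term, leaves it out without a reason.

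A programmer who follows the SAP literally would count a tongue-spasm-only subject in the Dystonia row and in no EPS row. The clinical study report could then show someone with dystonia who is not an EPS case. The error runs one way: leaving out a term can lower the EPS count but never raise it. Protocol 4.2 anticipates few extrapyramidal symptoms with this drug, so an undercount falls in the direction that agrees with the expectation.

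**Working it through.** There is no sample size, power or error-rate figure to reproduce here. The check is a comparison of lists, followed by the effect of one affected subject.

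**Step 1: compare the lists** (SAP 2.6.4 against Attachment 4.5.1)

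| Source group | Terms | In 4.5.1 | Not in 4.5.1 |
|---|---|---|---|
| Dystonia (2.6.4) | 6 | 5 | tongue spasm |
| Parkinsonism (2.6.4) | 7 | 7 | none |
| Both | 13 | 12 | 1 |

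The attachment has 17 terms. The other 17 − 12 = 5 are akathisia, dyskinesia, tardive dyskinesia, psychomotor hyperactivity and salivary hypersecretion. The entry that reads OCULOGLYRIC CRISIS in the text available to us was taken as a match for oculogyric crisis.

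The four explained exclusions are tremor, muscle rigidity, cogwheel rigidity and restlessness. None of them is tongue spasm.

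With the term added, the list has 17 + 1 = 18 terms. Non-akathisia terms rise from 17 − 1 = 16 to 17.

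**Step 2: effect of one affected subject on incidence**

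Inputs are the enrolled numbers in SAP 1.2.1: 271 + 125 + 306 = 702. All enrolled subjects are assumed to have been dosed, so that these numbers stand in for the safety population. The change in percentage points is 100 × 1/N.

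**Step 3: effect of one affected subject on the exposure-adjusted rate**

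The SAP does not define the denominator. Total person-time is assumed, not censored at the first event.

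- Planned duration: T = 104 × 7 / 365.25 = 1.993 years.
- The SAP's attrition of about 30% over six months is assumed to continue at a constant hazard to Week 104: h = −ln(0.70)/0.5 = 0.713 per year.
- Mean person-years per subject: (1 − exp(−hT))/h = 1.064. Pooled: 702 × 1.064 ≈ 747.
- Assumed range: no attrition gives 702 × 1.993 ≈ 1,399 person-years pooled. Attrition of 45% per six months gives h = −ln(0.55)/0.5 = 1.196, hence 0.759 years per subject and about 533 person-years pooled.

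The change per 100 person-years (PY) is 100/PY.

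| Group | N | Fall in incidence (points) | PY, central | Fall in rate per 100 PY, central | Range |
|---|---|---|---|---|---|
| Pooled | 702 | 0.14 | 747 | 0.13 | 0.07 to 0.19 |
| D1050301 | 271 | 0.37 | 288 | 0.35 | 0.19 to 0.49 |
| D1050325 | 125 | 0.80 | 133 | 0.75 | 0.40 to 1.05 |
| D1050326 | 306 | 0.33 | 326 | 0.31 | 0.16 to 0.43 |

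The incidence effect scales with the number of affected subjects. As an illustration, three of them would lower pooled incidence by 100 × 3/702 = 0.43 points; none would lower it by 0. A subject who has tongue spasm together with any listed term is still counted as EPS.

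**The case against.** The strongest case against is that no rule is broken. Nothing in the SAP says that Dystonia must be nested within EPS, and the two lists serve different summaries. The attachment already contains terms that belong to neither combined group. The special-interest terms also come from medical review of coded events, so tongue spasm may be absent simply because nobody had it. That review could still correct the list before lock 2. In addition, the event stays visible: "Summaries of AEs by preferred term only by analysis group for both combined and uncombined terms will be generated as well, respectively". Finally, the two interim analyses had their own SAPs, which are not available here. If they used the same 17 terms, consistency could be a reason to leave the list alone.

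Much of this limits the size of the problem but does not remove it. It is true that nesting is inferred, that the effect may be zero, and that the review is the natural place for the correction. But the SAP took care to explain four exclusions and gave none for this term, while 12 of 13 terms do carry over. A provision for review is not evidence that the change was made. If no event was coded, adding the term changes no result and simply aligns the definitions. Comparability with the interim reports can be handled by disclosure.

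The table was machine-read and its last row has one entry, but 17 terms in two columns would leave exactly one blank cell. Nothing suggests lost text.

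**Conclusion.** The concern holds. Tongue spasm is the only one of the 13 dystonia and parkinsonism terms that the EPS list leaves out, and no stated reason covers it. Applied literally, the rule gives an undercount in one direction in the EPS incidence, the exposure-adjusted rate, the non-akathisia row and, where produced, the EPS summary by exposure.

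The size is small. The number of affected subjects is unknown and may be zero; per affected subject the effect is a fraction of a percentage point in every cohort. The incidence figures rest on all enrolled subjects having been dosed. The rate figures rest also on the assumed attrition pattern and denominator, and should be read as orders of magnitude. The primary safety variables (Protocol 14.4.1) are unaffected. The set comparison is certain; that the omission was an oversight is an inference, though the likelier reading. This is an optional improvement, not an obstacle to the analysis.

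**What to change.** Add tongue spasm to Attachment 4.5.1 before final database lock 2, targeted in SAP section 1 for November 21, 2018, and build the EPS tables for all three cohorts in the full report from the resulting 18 terms. If the medical review finds that the omission was deliberate, the SAP should state the reason instead.

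With the term added, include one programming check: the number of subjects counted under Dystonia or Parkinsonism but not under EPS must be 0. The same check would reveal a failed text match from the spelling of oculogyric crisis in the attachment.

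The cost is one term and one check. The final lock 2 tables for D1050325 and D1050326 do not exist yet, so nothing is re-run for those cohorts. The drawback concerns D1050301: SAP section 1 says lock 1 has occurred and that cohort's report is complete, although SAP 2.1.1 still describes lock 1 as expected. If a tongue-spasm-only subject exists there, the EPS count will differ between the two reports and needs a footnote. It would be sensible to note the list change in the full report even if no count moves, and to say whether the interim reports used the 17-term list. The errata route in SAP 2.1.1 covers data errors, so a changed definition needs its own note.
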